#### **6.3.4 Early Termination Visit**

The V4 assessments and DCFs (see [Section 6.3.3](#)) must be completed at the early termination visit for participants who withdraw, or are withdrawn, or terminated from the study. If a participant withdraws between scheduled visits, the participant will be asked to return to the clinic to perform the V4 assessments.

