## 6.4 Unscheduled Study Visits

Unscheduled visits may occur at any time during the study. For example, for problems with the study medication or development of intercurrent vaginal symptoms. Any of the following activities will be performed at the discretion of the site PI:

- Medical history will be reviewed and updated as appropriate.
- Interim sexual history since the last clinic visit will be collected.
- Vaginal symptoms will be assessed.
- A urine pregnancy test will be performed on all participants of childbearing potential.
- Compliance with the study protocol criteria will be assessed; any used and unused study IP packaging will be collected as relevant and recorded.
- Participant memory aid will be collected and reviewed.
- All concomitant medications taken since the last study visit will be recorded on the appropriate DCF. Previously recorded medications will be updated as appropriate.
- Study personnel will discuss with participants and assess and record all AEs/SAEs. Previously recorded AEs/SAEs will be updated as appropriate.
- If clinically indicated, a targeted physical examination will be performed by a qualified study clinician.
- A pelvic examination to include examination of external genitalia will be conducted, and swabs and samples taken for analysis of Amsel criteria; KOH and saline microscopy for identification of yeast forms, trichomonas, and clue cells; and Gram staining. Instructions for obtaining vaginal swab specimens for these assessments are outlined in the protocol specific MOP. Gram stain Nugent scoring will be conducted in the Central Laboratory; all other testing will be conducted locally.
- Participants with clinical evidence of VVC based on vulvovaginal signs (edema, erythema, and/or excoriation) and symptoms (vulvovaginal itching, burning, and/or irritation) will have a confirmatory vaginal *Candida* culture and treated as appropriate with oral fluconazole. Participants who cannot take oral fluconazole will be terminated from the study.
- Vulvovaginal signs will be assessed and graded by severity, as applicable. A clinical determination for BV recurrence will be made based on evaluation of Amsel criteria. The

---

presence of  $>2$  of 4 Amsel criteria is required for a diagnosis of BV recurrence. Participants with a clinical diagnosis of BV recurrence will complete a satisfaction questionnaire and will be terminated from the study.

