4.5. Efficacy (Immunogenicity) and Safety Variables

Multiple observations within specific visit period are acceptable. In the case of multiple observations within a specific window, the assessment value that is closest to the scheduled visit window will be used in the analyses for the post-baseline records. Whether to use and how to use the observations from early termination at an unscheduled visit along with the observations obtained at the corresponding scheduled visit will be specified in the applicable tables. For screening and baseline visits, the last assessment value will be used. All the recorded data will be listed. If observations have the same distance to the scheduled assessment, the latest one will be used.

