Early Discontinuation from Treatment ^d	x	xx	x	xx	x	xx
Early Termination from Study ^b	x	xx	x	xx	x	xx

^a Received Treatment includes subjects who successfully received at least one dose of study treatment. It is unknown whether subjects received at least one dose if they were terminated early before Visit 2 and a Study Product Dispensing assessment at the early termination visit could not be conducted.

^b Completed Follow-up includes subjects who remained BV suppressed and were followed-up through Visit 4 as well as subjects whose participation ended prior to Visit 4 due to a clinical BV diagnosis. Terminated Early includes subjects who terminated from the study early for reasons other than a clinical BV diagnosis.

^c A blinded case review committee reviewed subjects' data to determine treatment compliance throughout the study for each subject.

^d Subjects who discontinued treatment due to RBV are included.

Table 4: Analysis Populations by Treatment Group

Analysis Populations	Reason Subjects Excluded	TOL-463 Vaginal Insert (N=X)		Placebo (N=X)		All Subjects (N=X)	
		n	%	n	%	%	n
Eligible for Safety Analysis Population	N/A	x	xx	x	xx	x	xx
Excluded from Safety Analysis Population	Any Reason	x	xx	x	xx	x	xx
	Did not receive at least one dose of study product	x	xx	x	xx	x	xx
Eligible for Modified Intent-to-Treat Analysis (mITT) Population	N/A	x	xx	x	xx	x	xx
Excluded from for Modified Intent-to-Treat Analysis (mITT) Population	Any Reason	x	xx	x	xx	x	xx
	Positive NAAT test results at baseline for C. trachomatis, N. gonorrhoeae, or T. vaginalis	x	xx	x	xx	x	xx
	HPV Criterion ^a	x	xx	x	xx	x	xx
Eligible for Per-Protocol (PP) Analysis Population	N/A	x	xx	x	xx	x	xx
Excluded from Per-Protocol (PP) Analysis Population	Any Reason	x	xx	x	xx	x	xx
	Did not meet inclusion/exclusion criteria	x	xx	x	xx	x	xx
	Positive NAAT test results at baseline for C. trachomatis, N. gonorrhoeae, or T. vaginalis	x	xx	x	xx	x	xx
	HPV Criterion ^a	x	xx	x	xx	x	xx
	Was not compliant with study product	x	xx	x	xx	x	xx
	Did not return to study site for the TOC visit within the specified window (Visit 4, Day 85-91)	x	xx	x	xx	x	xx
	Was not followed up to the diagnosis of recurrent BV	x	xx	x	xx	x	xx

Notes: N=Number of all enrolled subjects

^a For participants 21 years of age or older, documentation of or self-report of abnormal, or ASCUS HPV Positive Pap test prior to screening, or Pap smear performed at screening/enrollment with abnormal result.

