Table 11: Summary of Amsel Criteria by Study Visit and Treatment group – mITT Population

Amsel Criteria	Subcategories and Summary Statistics	TOL-463 Vaginal Insert (N = xxx)				Placebo (N = xxx)				All Subjects (N = xxx)			
		Visit 1 (N = xxx)	Visit 2 (N = xxx)	Visit 3 (N = xxx)	Visit 4 (N = xxx)	Visit 1 (N = xxx)	Visit 2 (N = xxx)	Visit 3 (N = xxx)	Visit 4 (N = xxx)	Visit 1 (N = xxx)	Visit 2 (N = xxx)	Visit 3 (N = xxx)	Visit 4 (N = xxx)
Presence of Amsel Criteria	0/4 (%)	x	x	x	x	x	x	x	x	x	x	x	x
	1/4 (%)	x	x	x	x	x	x	x	x	x	x	x	x
	2/4 (%)	x	x	x	x	x	x	x	x	x	x	x	x
	3/4 (%)	x	x	x	x	x	x	x	x	x	x	x	x
	4/4 (%)	x	x	x	x	x	x	x	x	x	x	x	x
pH	>4.5 (%)	x	x	x	x	x	x	x	x	x	x	x	x
	Mean	x.xx	x.xx	x.xx	x.xx	x.xx	x.xx	x.xx	x.xx	x.xx	x.xx	x.xx	x.xx
	Standard Deviation of Mean	x.xx	x.xx	x.xx	x.xx	x.xx	x.xx	x.xx	x.xx	x.xx	x.xx	x.xx	x.xx
	Mean Change from Visit 1	N/A	x.xx	x.xx	x.xx	N/A	x.xx	x.xx	x.xx	N/A	x.xx	x.xx	x.xx
	Standard Deviation of Mean Change from Visit 1	N/A	x.xx	x.xx	x.xx	N/A	x.xx	x.xx	x.xx	N/A	x.xx	x.xx	x.xx
Clue Cells >=20%	Present (%)	x	x	x	x	x	x	x	x	x	x	x	x
Amine ("whiff") test on KOH wet mount	Positive (%)	x	x	x	x	x	x	x	x	x	x	x	x
Homogenous vaginal discharge characteristic of BV	Yes (%)	x	x	x	x	x	x	x	x	x	x	x	x

Notes: N=Number of subjects in the mITT population in the specified group and timepoint.

Data from the previous enrollment(s) of a repeat subject are excluded.

Observations from early termination at an unscheduled visit will be summarized into the preceding scheduled visit. From the scheduled visit and the corresponding unscheduled early termination visit, use the visit with the maximum number of present Amsel criteria for Presence of Amsel Criteria and report each corresponding Amsel criterion from that visit.

Table 12: Summary of Amsel Criteria by Study Visit and Treatment group – PP Population

Amsel Criteria	Subcategories and Summary Statistics	TOL-463 Vaginal Insert (N = xxx)				Placebo (N = xxx)				All Subjects (N = xxx)			
		Visit 1 (N = xxx)	Visit 2 (N = xxx)	Visit 3 (N = xxx)	Visit 4 (N = xxx)	Visit 1 (N = xxx)	Visit 2 (N = xxx)	Visit 3 (N = xxx)	Visit 4 (N = xxx)	Visit 1 (N = xxx)	Visit 2 (N = xxx)	Visit 3 (N = xxx)	Visit 4 (N = xxx)
Presence of Amsel Criteria	0/4 (%)	x	x	x	x	x	x	x	x	x	x	x	x
	1/4 (%)	x	x	x	x	x	x	x	x	x	x	x	x
	2/4 (%)	x	x	x	x	x	x	x	x	x	x	x	x
	3/4 (%)	x	x	x	x	x	x	x	x	x	x	x	x
	4/4 (%)	x	x	x	x	x	x	x	x	x	x	x	x
pH	>4.5 (%)	x	x	x	x	x	x	x	x	x	x	x	x
	Mean	x.xx	x.xx	x.xx	x.xx	x.xx	x.xx	x.xx	x.xx	x.xx	x.xx	x.xx	x.xx

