Symptoms and Signs	Symptoms Subcategories	TOL-463 Vaginal Insert (N=X)					Placebo (N=X)					All Subjects (N=X)				
		Visit 0	Visit 1	Visit 2	Visit 3	Visit 4	Visit 0	Visit 1	Visit 2	Visit 3	Visit 4	Visit 0	Visit 1	Visit 2	Visit 3	Visit 4
Abnormal Vaginal Discharge	n	n	n	n	n	n	n	n	n	n	n	n	n	n	n	n
	No	x	x	x	x	x	x	x	x	x	x	x	x	x	x	x
	Yes, consistent with BV	x	x	x	x	x	x	x	x	x	x	x	x	x	x	x
	Yes, other	x	x	x	x	x	x	x	x	x	x	x	x	x	x	x
Vaginal Odor	n	n	n	n	n	n	n	n	n	n	n	n	n	n	n	n
	No	x	x	x	x	x	x	x	x	x	x	x	x	x	x	x
	Yes, consistent with BV	x	x	x	x	x	x	x	x	x	x	x	x	x	x	x
	Yes, other	x	x	x	x	x	x	x	x	x	x	x	x	x	x	x

Notes: N=Number of subjects in the mITT population in the specified group.

Subjects will be further excluded if no data is available at the specified timepoint, n=Number of subjects with available data for the specified category at the specified timepoint, and these counts are shown in the row of n, whereas the data shown in the rows of each response level in this table are percentages, where n is the denominator.

For post-enrollment visits, observations from early termination at an unscheduled visit will be summarized into the preceding scheduled visit. For Vaginal Discharge and Odor responses from the scheduled visit and the corresponding unscheduled early termination visit, count the subject in “Yes, consistent with BV” when at least one response was “Yes, consistent with BV”; count the subject in “Yes, other” when no response was in “Yes, consistent with BV” and at least one response was from “Yes, other”; count the subject in “No” when all responses were “No”.

Table 16: Summary of Proportion of Participants Reporting BV Symptoms – PP Population

Symptoms and Signs	Subcategories	TOL-463 Vaginal Insert (N=X)					Placebo (N=X)					All Subjects (N=X)				
		Visit 0	Visit 1	Visit 2	Visit 3	Visit 4	Visit 0	Visit 1	Visit 2	Visit 3	Visit 4	Visit 0	Visit 1	Visit 2	Visit 3	Visit 4
Abnormal Vaginal Discharge	n	n	n	n	n	n	n	n	n	n	n	n	n	n	n	n
	No	x	x	x	x	x	x	x	x	x	x	x	x	x	x	x
	Yes, consistent with BV	x	x	x	x	x	x	x	x	x	x	x	x	x	x	x
	Yes, other	x	x	x	x	x	x	x	x	x	x	x	x	x	x	x
Vaginal Odor	n	n	n	n	n	n	n	n	n	n	n	n	n	n	n	n
	No	x	x	x	x	x	x	x	x	x	x	x	x	x	x	x
	Yes, consistent with BV	x	x	x	x	x	x	x	x	x	x	x	x	x	x	x
	Yes, other	x	x	x	x	x	x	x	x	x	x	x	x	x	x	x

Notes: N=Number of subjects in the PP population in the specified group.

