Treatment Group: , Subject ID: , AE Number:											
Comments:											
Treatment Group: , Subject ID: , AE Number:											
Comments:											

Table 36: Occurrence of Culture Confirmed Secondary Vulvovaginal Candidiasis (VVC) Overall and by Treatment Groups – Safety Population

Treatment Group	Number of Subjects N	Number of Subjects with VVC ^a n	Proportion of Subjects with VVC	Proportion of Subjects with VVC 95% CI ^b	Difference in Proportion of Subjects with VVC between Treatment Arms	Difference in Proportion of Subjects with VVC between Treatment Arms 95% CI ^c
TOL-463 Vaginal Insert	x	x	0.xx	0.xx, 0.xx		
Placebo	x	x	0.xx	0.xx, 0.xx	0.xx	0.xx, 0.xx

Notes: The denominator for proportions is based on the number of subjects who used at least one insert in the respective treatment group.

^a The occurrence of culture confirmed secondary VVC following initiation of study treatment and through the final study visit is calculated. Subjects enrolled with concurrent VVC at baseline (visit 1) that can be treated with oral fluconazole is not counted towards n.

^b 95% Wilson confidence interval for the proportion of subjects with VVC.

^c 95% Newcombe confidence interval for difference in proportions between arms.

Table 37: Summary of Proportion of Participants Reporting Vulvovaginal Symptoms and Signs, Yeast Form, and Clinical Diagnosed and Culture Confirmed Vulvovaginal Candidiasis – Safety Population

Symptoms/Signs Severity	TOL-463 Vaginal Insert (N=X)					Placebo (N=X)					All Subjects (N=X)				
	Visit 0	Visit 1	Visit 2	Visit 3	Visit 4	Visit 0	Visit 1	Visit 2	Visit 3	Visit 4	Visit 0	Visit 1	Visit 2	Visit 3	Visit 4
Burning															
n	n	n	n	n	n	n	n	n	n	n	n	n	n	n	n
None	x	x	x	x	x	x	x	x	x	x	x	x	x	x	x
Mild	x	x	x	x	x	x	x	x	x	x	x	x	x	x	x
Moderate	x	x	x	x	x	x	x	x	x	x	x	x	x	x	x
Severe	x	x	x	x	x	x	x	x	x	x	x	x	x	x	x
Irritation															
n	n	n	n	n	n	n	n	n	n	n	n	n	n	n	n
None	x	x	x	x	x	x	x	x	x	x	x	x	x	x	x
Mild	x	x	x	x	x	x	x	x	x	x	x	x	x	x	x
Moderate	x	x	x	x	x	x	x	x	x	x	x	x	x	x	x
Severe	x	x	x	x	x	x	x	x	x	x	x	x	x	x	x
Itching															
n	n	n	n	n	n	n	n	n	n	n	n	n	n	n	n
None	x	x	x	x	x	x	x	x	x	x	x	x	x	x	x
Mild	x	x	x	x	x	x	x	x	x	x	x	x	x	x	x
Moderate	x	x	x	x	x	x	x	x	x	x	x	x	x	x	x
Severe	x	x	x	x	x	x	x	x	x	x	x	x	x	x	x
Edema															
n	n	n	n	n	n	n	n	n	n	n	n	n	n	n	n
Absent	x	x	x	x	x	x	x	x	x	x	x	x	x	x	x
Mild	x	x	x	x	x	x	x	x	x	x	x	x	x	x	x
Moderate	x	x	x	x	x	x	x	x	x	x	x	x	x	x	x
Severe	x	x	x	x	x	x	x	x	x	x	x	x	x	x	x

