Symptoms/Signs Severity	TOL-463 Vaginal Insert (N=X)					Placebo (N=X)					All Subjects (N=X)				
	Visit 0	Visit 1	Visit 2	Visit 3	Visit 4	Visit 0	Visit 1	Visit 2	Visit 3	Visit 4	Visit 0	Visit 1	Visit 2	Visit 3	Visit 4
Erythema															
n	n	n	n	n	n	n	n	n	n	n	n	n	n	n	n
Absent	x	x	x	x	x	x	x	x	x	x	x	x	x	x	x
Mild	x	x	x	x	x	x	x	x	x	x	x	x	x	x	x
Moderate	x	x	x	x	x	x	x	x	x	x	x	x	x	x	x
Severe	x	x	x	x	x	x	x	x	x	x	x	x	x	x	x
Excoriation															
n	n	n	n	n	n	n	n	n	n	n	n	n	n	n	n
Absent	x	x	x	x	x	x	x	x	x	x	x	x	x	x	x
Mild	x	x	x	x	x	x	x	x	x	x	x	x	x	x	x
Moderate	x	x	x	x	x	x	x	x	x	x	x	x	x	x	x
Severe	x	x	x	x	x	x	x	x	x	x	x	x	x	x	x
KOH Wet Mount Microscopy: Yeast (budding, branching, hyphae)															
n	n	n	n	n	n	n	n	n	n	n	n	n	n	n	n
Absent	x	x	x	x	x	x	x	x	x	x	x	x	x	x	x
Present	x	x	x	x	x	x	x	x	x	x	x	x	x	x	x
Clinical Diagnosis of Vulvovaginal Candidiasis															
n	N/A	n	n	n	n	N/A	n	n	n	N/A	n	n	n	n	n
Yes	N/A	x	x	x	x	N/A	x	x	x	N/A	x	x	x	x	x
No	N/A	x	x	x	x	N/A	x	x	x	N/A	x	x	x	x	x
Culture Confirmed Vulvovaginal Candidiasis															
n	N/A	n	n	n	n	N/A	n	n	n	N/A	n	n	n	n	n
Yes	N/A	x	x	x	x	N/A	x	x	x	N/A	x	x	x	x	x
No	N/A	x	x	x	x	N/A	x	x	x	N/A	x	x	x	x	x

Symptoms/Signs Severity	TOL-463 Vaginal Insert (N=X)					Placebo (N=X)					All Subjects (N=X)				
	Visit 0	Visit 1	Visit 2	Visit 3	Visit 4	Visit 0	Visit 1	Visit 2	Visit 3	Visit 4	Visit 0	Visit 1	Visit 2	Visit 3	Visit 4

Notes: N=Number of subjects in the Safety population in the specified group.

Subjects will be further excluded if no data is available at the specified timepoint, n=Number of subjects with available data for the specified category at the specified timepoint, and these counts are shown in the row of n, whereas the data shown in the rows of each response level in this table are percentages, where n is the denominator.

Observations from early termination at an unscheduled visit will be summarized into the preceding scheduled visit. For Burning, Irritation, Itching, Edema, Erythema, and Excoriation, the maximum severity level from the scheduled visit and the corresponding unscheduled early termination visit will be counted. For KOH wet mount Microcopy responses from the scheduled visit and the corresponding unscheduled early termination visit, count the subject in "Present" when at least one response was "Present", and count "Absent" when all responses were "Absent".

Table 38: Additional Pelvic Examination Measures

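### The notes to SAP Tables 11, 37 and 38 let findings from an early termination between Visits 1 and 2 print in the pre-dose Visit 1 column

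*SAP*

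**What the plan says.** Three table shells in SAP Appendix 1 share one placement sentence: "Observations from early termination at an unscheduled visit will be summarized into the preceding scheduled visit". They are Table 11 (Amsel criteria, mITT), Table 37 (vulvovaginal signs and symptoms, yeast and VVC, Safety) and Table 38 (genital lesions and trichomonads, Safety). All three have a Visit 1 column, and Tables 37 and 38 also have a Visit 0 column.

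Each note adds a rule for combining the two visits:
- **Table 11** takes the visit with more Amsel criteria and reports the individual criteria from that visit.
- **Table 37** says, for the six graded signs and symptoms, that "the maximum severity level from the scheduled visit and the corresponding unscheduled early termination visit will be counted". KOH microscopy is present if either visit shows it.
- **Table 38** likewise counts a finding as present if either visit shows it.

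The Table 15 note has nearly the same sentence with a limit in front: "For post-enrollment visits, observations from early termination at an unscheduled visit will be summarized into the preceding scheduled visit".

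SAP 4.5 leaves the handling of these observations to the individual tables. On baseline it says only: "For screening and baseline visits, the last assessment value will be used".

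**The concern.** Visit 1 is the enrollment visit. Under Protocol 6.2 the pelvic examination comes first and study product is handed out afterwards, so a reader takes the Visit 1 column as the state before treatment. If a woman's participation ends at an unscheduled visit after Visit 1 and before Visit 2, the scheduled visit that precedes it is Visit 1. Read as written, the notes merge her later record into that column and keep whichever finding is worse.

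Burning and itching are rows of Table 37, and Protocol 2.3.1.1 names vulvovaginal burning and pruritus as examples of the commonest treatment-related events. A local reaction severe enough to end participation early is therefore the kind of finding that could be shown as a baseline state. In Table 38, a new genital lesion found at such a visit would read as present at Visit 1, where an active lesion is an enrollment exclusion (Protocol 5.1.2.2). The table would then suggest an eligibility violation that did not happen.

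**Working it through.** The plan states no figure on this point. The check is to trace the rule and then size one misplaced record.

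**1. Can such a record arise?** The direct route is Protocol 6.4. A woman with clinical evidence of VVC at an unscheduled visit is cultured and treated, and "Participants who cannot take oral fluconazole will be terminated from the study". Nothing confines this to the period after Visit 2.

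Two other places support this only indirectly:
- The Table 3 footnote contemplates women who were "terminated early before Visit 2 and a Study Product Dispensing assessment at the early termination visit could not be conducted". Their dosing is unknown, so they are outside the Safety population and cannot appear in Tables 37 or 38.
- Protocol 6.3.4 says: "If a participant withdraws between scheduled visits, the participant will be asked to return to the clinic to perform the V4 assessments". The schedule of events gives that visit its own column, separate from unscheduled visits.

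**2. Does another rule stop it?** SAP 4.5 defers to the table notes. Its last-value rule for baseline is not tied to first dose, so it gives no protection.

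**3. Table 11, non-BV termination before Visit 2.** Eligibility allows 0, 1 or 2 criteria at Visit 1 (Protocol 5.1.1.2). A termination for a reason other than BV also has 0, 1 or 2. That gives 3 × 3 = 9 pairs:
- The termination record is worse and replaces Visit 1 in 3 pairs (0 to 1, 0 to 2, 1 to 2).
- Visit 1 is kept in 3 pairs (1 to 0, 2 to 0, 2 to 1).
- The other 3 are ties, and the note does not say which visit's individual criteria are printed.

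**4. Tables 37 and 38.** A higher severity, or a finding present at the termination visit only, replaces the Visit 1 value. For culture and for the clinical diagnosis of VVC, the Table 37 note gives no combining rule.

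**5. Table 36 against Table 37.** Table 36 counts culture-confirmed VVC after treatment starts, and its footnote adds: "Subjects enrolled with concurrent VVC at baseline (visit 1) that can be treated with oral fluconazole is not counted towards n". A new positive culture before Visit 2 counts there as secondary VVC. If the general placement sentence also reaches culture, Table 37 would show the same culture under Visit 1. The conflict is conditional on that reading.

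**6. Size per record.** In a categorical row where the woman already has a Visit 1 value, the denominator does not change and one count moves. The shift is 100/n percentage points, with n the row's own denominator:
- n = 125 (planned enrolled per arm, SAP 4.1): 100/125 = 0.8
- n = 100 (200 planned evaluable, two arms): 100/100 = 1.0
- n = 50 (assumed, because SAP 5 reports early closure without the actual n): 100/50 = 2.0

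For an assumed k = 1 to 10 such women in one arm, 100k/n runs from 0.8 to 8.0 points at n = 125 and from 1.0 to 10.0 at n = 100. SAP 13 prints percentages as whole numbers, so at the planned sizes one record is about one printed unit.

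**7. Where 100/n fails.** Listing 19 marks culture as not applicable when there was no clinical diagnosis, so the culture row's n is only the women cultured. A woman not cultured at Visit 1 would enter both numerator and denominator. With an assumed 2 of 4 positive, adding her gives 3 of 5, or 50% to 60%: a shift of 10 points, which is neither 100/4 nor 100/5. Mean pH would move by (termination pH − Visit 1 pH)/n, which depends on the values. The pH change rows are not affected through her, because she has no later visit from which to compute a change.

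**The case against.** The strongest case against the point is that this is a gap in shell wording with thin evidence that any woman is affected. Much of that stands. The Table 3 footnote and Protocol 6.3.4 are indirect support, so one direct route remains, of unknown frequency. Protocol 2.3.1.1 reports that no related adverse event led to discontinuation in earlier trials. Tables 21 and 22 give a baseline VVC status with no such mapping, and Listings 6, 8, 19 and 20 show the actual study day. The Table 15 qualifier could describe the observations being moved as well as the column receiving them, so an omission from the other three notes is an inference about the cause. None of this supplies the missing exclusion: a programmer who follows the three notes would still write post-dose data into Visit 1.

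A reader might infer more than the documents support:

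- *That eligible women would show 3 or 4 Amsel criteria at Visit 1.* This would follow only if the notes cover in-study BV recurrences, since 3 or 4 always exceeds the Visit 1 limit of 2. The documents point both ways. SAP 3.3 counts those women as completers. The PP shells (Tables 12 and 16) carry no mapping note, although under SAP 6.3 recurrence is the only way a PP participant ends before Visit 4. Against that, Table 11 has a maximum-Amsel rule, Protocol 6.4 describes recurrences as terminated from the study, and the Listing 6 note expects an unscheduled visit to be a termination visit.
- *That Tables 36 and 37 must contradict each other.* This depends on whether the placement sentence reaches culture.
- *That the efficacy comparison is compromised.* The primary analysis does not use this mapping.

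**Conclusion.** The rule is wrong as written in the notes to Tables 11, 37 and 38: it can place findings made after the first dose in a pre-dose column. The concern is minor, because only descriptive by-visit displays are affected. Tables 6 to 10, the Kaplan-Meier analysis, the adverse event tables, Table 36, the baseline VVC rows of Tables 21 and 22, and Listings 6, 8, 19 and 20 are untouched.

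The number of women is unknown, and so is the total effect. Per record the shift is 100/n points in the categorical rows described above, and a record that is not worse than the Visit 1 result does not raise the row. Confidence is high that the exclusion is missing and that nothing else supplies it. The conflict between Tables 36 and 37, and any coverage of BV recurrences, remain conditional on readings that the sponsor has to settle.

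**What to change.** Add one rule to the notes of Tables 11, 37 and 38, and make it explicit in Table 15: no observation taken after Visit 1 enters the Visit 0 or Visit 1 column. Because that leaves terminations before Visit 2 without a column, show them separately, for example in a labelled Early Termination column or as a footnoted count. Listings 8, 19 and 20 already give early termination its own row. The mapping of later terminations can stay.

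In the same edit:
- state whether the notes cover in-study BV recurrences found at unscheduled visits, and carry the rule to Tables 12 and 16 only if they do;
- say how culture and clinical VVC diagnosis are combined in Table 37;
- say which visit is printed when the Amsel counts in Table 11 tie.

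The cost is a few words in four notes and a small change to the visit-mapping program. No inferential analysis changes.
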